## 14.11 Access to the Final Study Dataset

The raw data contained in the eCRF will belong to the Sponsor. Only those members of the Sponsor team who are actively involved in performing the statistical analysis to produce the results for the study will be granted access to the final study dataset.

The investigational site team at CUH will be given the results of the study but will not have access to the raw data.

Study participants will have been asked as part of the informed consent process whether they agree to their anonymised data being used for future research purposes. If consent has been provided, the relevant raw data could be made available to the CI, providing separate approvals have been granted for such further research purposes.

#### 15.0 ADVERSE EVENTS AND REPORTING

#### 15.1 Definition of an Adverse Event

An Adverse Event (AE) is any untoward medical occurrence, unintended disease or injury or any untoward clinical sign in a clinical investigational subject, temporally associated with the subject's participation in research, whether or not it is considered related to the investigational medical device. This includes events related to the investigational medical device (IMD) or the comparator, and events related to the procedures involved in the clinical investigation plan. The Common Terminology Criteria for Adverse Events (CTCAE) v5.0 will be used to determine the most appropriate medical term for the AE (see Appendix 9).

## 15.2 Definition of a Serious Adverse Event (SAE)

A Serious Adverse Event (SAE) is any untoward medical occurrence that has results in any of the following:

- 1) Death
- 2) Life-threatening illness or injury
- 3) In-patient hospitalisation or prolongation of existing hospitalisation
- 4) Permanent impairment of a body structure or body function
- 5) Congenital abnormality or birth defect.

### 15.3 Definition of an Adverse Device Effect (ADE)

An Adverse Device Effect (ADE) is an Adverse Event (AE) related to use of an investigational medical device. This includes any AE resulting from insufficiencies or

inadequacies in the instructions for the use, deployment, operation or any malfunction of the investigational medical device. This includes any AE that is a result of a user error or intentional misuse of the device.

## 15.4 Definition of Device Deficiency (DD)

Device deficiency (DD) is the inadequacy of a medical device related to its identity, quality, durability, reliability, safety or performance, such as malfunction, misuse or use error and inadequate labelling. All occurrences of Device Deficiencies must be reported to the Sponsor using a DD Reporting Form (blank DD reporting forms will be provided to the site in the ISF).

#### 15.5 Definition of a Serious Adverse Device Effect (SADE)

A Serious Adverse Device Effect (SADE) is an adverse device effect that has resulted in any of the following consequences:

- 1) Death
- 2) Life-threatening illness or injury
- 3) In-patient hospitalisation or prolongation of existing hospitalisation
- 4) Permanent impairment of a body structure or body function
- 5) Congenital abnormality or birth defect.

#### 15.6 Definition of an Unanticipated Serious Adverse Device Effect (USADE)

An Unanticipated Serious Adverse Device Effect (USADE) is a Serious Adverse Device Effect which by its nature, incidence, severity or outcome has not been identified in the current version of the risk analysis report. All USADEs should be reported to the Sponsor using an SAE/SADE Reporting Form (see section 15.11).

## 15.7 Anticipated and Unanticipated Adverse Events

It is not anticipated that any AEs will occur during the testing of the medical device as the app utilises the smartphone's camera function to perform a non-invasive scan. Despite this, the reporting mechanism for site and Sponsor to handle any adverse events that do transpire is defined in this protocol to ensure all occurrences are captured and handled as necessary for patient safety and compliance with regulatory safety reporting requirements.

## 15.8 Classification of Adverse Event Causality

The CI is required to speculate as to the relationship between the SAE and the Investigational Medical Device (IMD), namely purpleDx. The classification of relationship is as follows:

- 1) Unrelated
- 2) Unlikely to be related
- 3) Possibly related
- 4) Probably related
- 5) Definitely related.

#### 15.9 Classification of Adverse Event Seriousness

The CI is required to classify the seriousness of the SAE/SADE using the CTCAE v5.0 for the most appropriate grading from 1 to 5, where 1 is less serious and 5 is more serious. It should be noted that the term 'seriousness' is not the same as 'severity'. An AE may be considered severe but could be of minor medical significance. An AE is only considered to be serious if it results in any of the points as listed in 15.2, such that an AE can be considered severe but not serious, and vice versa.

## 15.10 Classification of Adverse Event Severity

The CI is required to classify the severity of the SAE/SADE. The severity is related to the intensity of the event, usually classified as mild, moderate or severe.

## 15.11 Reporting Requirements for SAEs/SADEs

Every SAE/SADE (including Unexpected Serious Adverse Device Effects; USADEs) must be reported to the Sponsor. The CI/RN must submit an initial SAE/SADE report to the Sponsor as soon as possible (within 24 hours of knowledge of the SAE/SADE taking place). A follow up form should be submitted to update the Sponsor as to further information within 7 days and as more information is available until the conclusion of the SAE/SADE. Blank SAE/SADE Reporting Forms will be provided to the site in the ISF. A new form should be used for each SAE/SADE and when providing follow up details.

The Sponsor must submit an initial report for each SAE/SADE to the MHRA and REC whether or not it is considered to be related to the IMD (purpleDx). A follow up report for each incident should be submitted to the MHRA and REC to provide full details of the investigation and outcome of the SAE/SADE.

#### 16.0 ETHICS AND REGULATORY COMPLIANCE

Clinical studies taking place in the NHS setting require approval from a Research Ethics Committee (REC) and the Health Regulatory Authority (HRA), along with a Letter of No Objection from the MHRA and NHS Trust R+D approval, prior to the start of any study process or procedure.

## 16.1 Research Ethics Committee Approval

The Sponsor will seek approval (favourable opinion) for this clinical study from an appropriate Research Ethics Committee (REC) by completing and submitting Parts A and B of the online Integrated Research Application System (IRAS) forms.

The team at CUH will complete appropriate requirements to gain Health Research Authority (HRA) site-specific approval (SSA) to perform the clinical study at CUH. In parallel, approval will be sought from CUH Research and Development Department, which will include agreement of costings for undertaking and performing the study, and Clinical Trial Agreement.

#### 16.2 MHRA Approval

The Sponsor will inform the MHRA of their intention to undertake the clinical study. Following confirmation of receipt of this information, the MHRA has 60 days to issue a Letter of Objection. If such an objection is not received by the Sponsor within that timeframe, it will be considered that the MHRA has no objections to the protocol, thus constituting regulatory authorisation to proceed with the clinical study.

#### 16.3 Substantial Amendments to the Protocol

If the Sponsor amends the protocol in a way that it deems substantial, it will submit a Notice of Amendment to the REC to obtain approval for the amendment. The Sponsor will also inform the MHRA and site R+D department. The protocol changes cannot be implemented at site until all approvals have been received (unless required to ensure the safety of the study participant, in which case the change can be implemented immediately).

If the amendment is not deemed substantial, the Sponsor will inform the REC, MHRA and R+D department of the amendment for their records, but formal approval is not required. The amendment number and updated protocol version and date will be

recorded in section 4.0 of the protocol, along with description and reason for the change/s.

### 16.4 Study Documentation and Reporting Requirements

The site undertaking the clinical study will keep all correspondence with the REC and MHRA in their Investigation Site File (ISF). The CI will submit a Progress Report to the REC within 30 days of the start of the study, and an Annual Progress Report (APR) each year thereafter until the end of the study. The CI will submit an End of Study Report within one year of completion of the study, including any publications or study reports that have been produced. The CI will inform the REC if the study is terminated prematurely, explaining the reasons for this.

## 16.5 Data Protection and Patient Confidentiality

#### 16.5.1 Data Protection

As this clinical study collects, stores and processes de-identified patient information, the risk of re-identification has been minimised. The Sponsor does not have access to the key required to decode the study numbers, making it impossible for the data to be traced back to individual participants. While fully anonymized data falls outside the scope of the General Data Protection Regulation (GDPR), the seven core principles of the Data Protection Act 2018 have been considered and enacted during the study's conception. The clinical site team must abide by these principles to ensure proper handling and safeguarding of participant data throughout the study.

- 1) Lawfulness, fairness and transparency: Subjects will be made aware of the information that will be captured for the purposes of this study, how it will be used and who will have access to the data during the informed consent process.
- **2) Purpose limitation**: The data collected and generated by the study will only be used as outlined in this protocol. Data will not be manipulated or analysed in any other way. Data will be analysed to fulfil the aims of this clinical study and will not be used for any other purpose.
- **3) Data minimisation**: Only the specific data points outlined in this protocol to achieve the aims of the study will be recorded. No additional or unnecessary details will be noted.
- **4) Accuracy**: The data will be reviewed by a monitor to ensure information is accurate and reliable. Any errors or omissions will be rectified accordingly.

- **5) Storage limitation**: The study records and information must be kept for at least 10 years following marketing to comply with the regulations for marketing new medical devices. This is detailed in the patient information sheet and expanded upon during the informed consent process as required.
- **6) Integrity and confidentiality**: The Sponsor will provide a secure electronic repository for purpleDx data to be stored in the cloud. Access to this database will be password protected and restricted to those authorised Sponsor team members directly involved in the analysis process. Passwords will be allocated on an individual basis and will not be shared. Access to the database will be timestamped to provide an auditable record.
- **7) Accountability**: The Sponsor is ultimately accountable for ensuring the principles of the Data Protection Act are adhered to and will achieve this via monitoring and auditing mechanisms.

## 16.5.2 Patient Confidentiality

To maintain patient confidentiality, the subjects who take part in this clinical study will each be identified by a study number that will consist of a sequence of seven numbers that are randomly generated (by the Vitalograph spirometer) and assigned completely independently of the patient details. The study number will replace all Patient Identifiable Data (PID) for the purposes of the study, and the Sponsor will have no access to PID.

The clinical site will maintain a subject log with details to link the study number to a specific patient. This log will not be kept in the Investigator Site File (ISF) and will not be accessible by the Sponsor but will be used by the monitor to ensure the correct subject medical notes are reviewed for the purposes of SDV. The log containing the linking code to individual patients will be securely stored in a password protected and encrypted digital file, in a separate location to any study data. During the informed consent process, subjects will be made aware of the need for the external review of PID in their hospital medical records for the monitoring process, to validate the depersonalised data for the study. It will be reiterated that no PID will be held in the study databases or accessible by the Sponsor. In this respect, the clinical site remains the data custodian in terms of any PID, whilst the Sponsor is responsible for the depersonalised data collected for study purposes as defined in this protocol.

Each subject will be required to provide consent for the Sponsor's monitor to access their PID solely for monitoring purposes. The ISF will be kept secure in a locked office only accessible by members of the site study team.

Although there is no patient identifiable data in this study, there is the potential for identifiable details to be sent to the Sponsor in error (e.g. on an email). Accordingly, methodology is in place to handle such a scenario.

If a breach of patient confidentiality occurs, the person discovering the breach must contact the Sponsor's designated Data Protection Officer (DPO) within 24 hours of discovery to inform them of the details. The Sponsor will then act in accordance with their internal Data Security and GDPR Compliance procedure.

The Sponsor will assess whether the breach is likely to result in a high risk to the rights and freedom of the individual/s concerned. If classed as high risk, the DPO will inform the Information Commissioner's Office (ICO) within 72 hours of discovery of the breach, along with the individual/s concerned without undue delay.

The Sponsor will maintain a log of all personal data breaches that occur during the clinical study, whether they constitute high risk or not.

#### 16.6 Patient and Public Involvement

In line with the NIHR UK Standards for Public Involvement, previous versions of apps used during the development of purpleDx have been tested on 30 volunteers at CUH in December 2024 and a number of patients and members of the public at an outreach care home visit in May 2025. On these occasions, the participants found the new device to be acceptable to use and were happy to comply with the requirements of the preliminary testing procedures.

## 16.7 Peer Review

The protocol has been peer reviewed by a Clinician and a Statistician who are independent of and external to electronRx and CUH and are not involved in the study in any way. The Clinician has the necessary knowledge of the clinical services and issues involved with the management of patients with respiratory disease to comment on the protocol design and premise, and the Statistician has the expertise to comment on the protocol design and analysis techniques. As this is a small-scale study carrying little risk to participants, this level of peer review is deemed proportionate. Accordingly, no Data Monitoring Committee or Data Advisory Committee will be convened.

## 16.8 Audits and Inspections

## 16.8.1 Protocol compliance

The Essential Documents (all documentation in the ISF and subjects' source documentation) at the clinical site will be thoroughly reviewed by the study monitor to assess protocol compliance and validity of trial conduct. If the monitor detects any protocol deviations, these will be discussed with the Chief Investigator and relevant members of the site team to determine the reason for the deviation and to mitigate its future occurrence. Any deviations will be corrected where possible. If it is not possible to correct the deviation, the details will be highlighted to the Sponsor to determine whether data is still usable or should be eliminated from the analysis. The deviations will be classified as minor or major and will be recorded in the monitoring visit report. The study monitor will provide re-training to study team members following all protocol deviations. If a member of the study team continues to deviate from the requirements of the protocol despite attempts by the Sponsor to re-train the individual, the Sponsor may request a replacement person to carry out the role with any further participants.

The Sponsor understands that accidental protocol deviations can occur from time to time. If a member of the site team realises an accidental protocol deviation has occurred, they should immediately notify the Chief Investigator at site and the Sponsor representative, providing details of what has happened and how it differs from the approved protocol. The CI and Sponsor will discuss whether the deviation can be rectified in any way. If it is not possible to correct the error, the Sponsor will decide whether the data is still useful or whether it should be excluded from the analysis.

All protocol deviations (minor and major) must be documented for full transparency, using a Protocol Deviation Reporting Form (blank PD reporting forms will be provided in the ISF). A deviation will be considered major if the Sponsor deems it to have jeopardised the integrity of the data in any way. Details of major deviations will be reported to the Ethics Committee.

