## 11.1 Figure 1: Overview of Study Visit Process

The CI/RN or designee will observe the subject using purpleDx and will use a simple tick-box Likert scale to answer a series of five questions about their ability to use the device. Each subject will also be asked to answer the same five questions using the simple tick-box scale to rate their ease of using the app (see Appendix 8 Section A – Device Setup and Use).

The CI/RN or designee will answer 3 additional questions (see Appendix 8 Section B – Time and Workflow).

Lastly, the CI/RN or designee and each subject will be asked to complete two open feedback questions to provide details of any difficulties or issues encountered during the process for setup, performing the scan, obtaining and recording results (see Appendix 8 Section C – Open Feedback).

All responses and required study information will be recorded in each subject's medical records or agreed form of source documentation. Data from purpleDx will be automatically uploaded to the Sponsor's database in the cloud. This information will only be identifiable by the subject study number i.e. no Patient Identifiable Data (PID) will be included.

Upon completion of the subject's visit, the CI/RN or designee will transcribe the information from any source documentation into the electronic Case Record Form (eCRF) within pre-agreed timelines (e.g. within 1 week of the date of the study timepoint).

The source documentation will be made available for external monitoring to ensure accuracy and validity of data transcribed into the eCRF.

All source documentation and the ISF must be kept for at least 10 years after the device is last placed on the market to comply with the medical device marketing requirements of regulators following completion of the study. Archival processes will be agreed between CUH and the Sponsor as part of the negotiation process to establish the Clinical Trial Agreement and ensure access can be arranged if required in future for auditing purposes.

The Sponsor will provide a secure database to act as the eCRF for the study raw data. Access to the eCRF will be password protected, and no patient identifiable data will be held within the eCRF. Each subject will only be identifiable by subject study number.

To access the eCRF, each user will require access rights to be granted by the Sponsor.

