## 14.4 Sample Size Calculation

## **14.4.1 PEF Sample Size Calculation** (to show lower 95% CI bound ≥80%)

Study goal:

- True success proportion p1
- Null threshold (target to exceed) p0=0.80
- Type I error (2-sided): α=0.05
- Power:  $1-\beta=0.90$
- Use **Wilson score CI** to test whether lower bound ≥ 0.80.

Approximate approach (one-sample proportion power analysis)

We can approximate using a **one-sample proportion test** (binomial test of  $H_0$ : p = 0.80 vs  $H_1$ :  $p = p_1 > 0.80$ ):

$$n = rac{\left[z_{1-lpha/2}\sqrt{p_0(1-p_0)} + z_{1-eta}\sqrt{p_1(1-p_1)}
ight]^2}{(p_1-p_0)^2}$$

This gives the approximate number of *paired comparisons* (subjects) needed.

Where:

- $z1-\alpha/2=1.96$  for  $\alpha=0.05$
- $z1-\beta=1.2816$  for 90% power

Example calculation

Expected true agreement proportion p1=0.90.

Then:

$$p_0 = 0.80, \quad p_1 = 0.90 \ n = rac{(1.96\sqrt{0.8 imes 0.2} + 1.2816\sqrt{0.9 imes 0.1})^2}{(0.9 - 0.8)^2}$$

Computing:

$$\sqrt{0.8 \times 0.2} = 0.4, \quad \sqrt{0.9 \times 0.1} = 0.3$$

$$n = \frac{(1.96(0.4) + 1.2816(0.3))^2}{(0.1)^2} = \frac{(0.784 + 0.384)^2}{0.01} = \frac{1.168^2}{0.01} = \frac{1.364}{0.01} = 136.4$$

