#### 18.0 DATA COLLECTION, HANDLING AND VERIFICATION

#### 18.1 Figure 2: Overview of Data Flow

#### 18.2 Source Documentation and Data Verification

The clinical site will confirm the location where all data will be recorded for the clinical study. This original documentation of data is referred to as source documentation. The clinical site will keep the source documentation secure and will provide it for review and verification by the study monitor as required. The data generated by purpleDx for the Breath Scan will be displayed on the phone screen then automatically submitted to the secure cloud storage. This will constitute the original source data for the purpleDx Breath Scan readings, which will be converted into a pdf document and returned to the

site for filing in the subject's medical record. The site team is required to transcribe the readings displayed on the screen at the time of measurement onto the visit paper record to serve as a backup in case an error occurs in the electronic process. If no pdf document is available, the handwritten visit record will constitute the source document. If any discrepancies are noted between the pdf document and the handwritten visit record, the Sponsor will be notified and asked to review the raw data to confirm correctness. If it is possible to provide the Pulse Scan measurements in a pdf document, this will also serve as the source document. However, if this is not possible, the handwritten visit record will constitute the source document.

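### Section 16.8.1 leaves exclusion of deviation data to the Sponsor case by case, with no pre-specified criteria, timing or blinding, and near the success boundary one or a few exclusions can reverse the primary result

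*Protocol*

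**What the plan says.** Protocol section 16.8.1 deals with deviations by two routes, and both end with the Sponsor. For one found by the monitor that cannot be corrected, "the details will be highlighted to the Sponsor to determine whether data is still usable or should be eliminated from the analysis". For one reported by the site, the Chief Investigator and the Sponsor discuss whether it can be rectified; if it cannot, "the Sponsor will decide whether the data is still useful or whether it should be excluded from the analysis". Whether a deviation counts as major is also the Sponsor's judgement. All deviations are documented on a form, and major ones go to the Ethics Committee.

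On who holds the data, section 11.1 says that purpleDx results upload automatically to the Sponsor's cloud database, and that "The Sponsor will provide a secure database to act as the eCRF for the study raw data". Section 16.9.1 makes the Sponsor responsible for the analysis. Sections 14.11 and 16.5.1 limit access to Sponsor staff involved in the analysis. Section 16.7 states that no monitoring committee will be convened.

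On the analysis, section 14.3.2 scores each subject as a success or failure against ±20% and calls the study positive if the lower Wilson bound is at least 80%. Section 14.7.3 uses complete cases. The estimand table (14.10) excludes invalid readings and makes a sensitivity analysis optional. No analysis set is defined by deviation status, and no analysis restores pairs removed under 16.8.1.

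**The concern.** The primary endpoint is one binary outcome per subject in an open, single-group comparison. Anyone who has both PEF values for a subject knows what excluding that subject does to the result. A rule that lets the device's manufacturer judge afterwards whether data are worth keeping, with no list of qualifying deviations and no separation from the measured values, leaves the denominator of the primary proportion open.

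If exclusions are unrelated to agreement, the proportion is not biased. If they fall more often on failing pairs, the proportion moves upward and the decision rule no longer has its nominal error rate. The result is meant to support a marketing application, and once discretionary exclusions have been made, its credibility cannot be fully restored. This is a rule that the protocol states, not a detail it leaves to a later plan.

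**Working it through.** **Inputs (Protocol 14.3.2 and 14.4.1).** "Type I error (2-sided): α=0.05"; "Null threshold (target to exceed) p0=0.80"; "Expected true agreement proportion p1=0.90"; power 0.90; 137 pairs required; 150 analysable sets sought from at most 160 recruits. The number of failing pairs dropped, k, is an assumption, because the protocol gives no deviation rate.

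**The plan's own figure.** n = [1.96 × 0.4 + 1.2816 × 0.3]² / 0.1² = (0.784 + 0.3845)² / 0.01 = 136.5, rounded up to 137. The printed 136.4 differs only by rounding, so the sample size reproduces.

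**The success rule as a count.** The Wilson lower bound for x successes in n pairs, with p̂ = x/n and z = 1.96, is

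L = [p̂ + z²/(2n) − z√(p̂(1−p̂)/n + z²/(4n²))] / (1 + z²/n).

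- 130/150: (0.8667 + 0.0128 − 0.0559) / 1.0256 = 0.803, passes.
- 129/150: (0.8600 + 0.0128 − 0.0570) / 1.0256 = 0.795, fails.
- 129/149 (one failing pair removed): (0.8658 + 0.0129 − 0.0562) / 1.0258 = 0.802, passes.

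With 150 pairs the rule therefore needs 130 successes. With no exclusions, the exact binomial chance of reaching 130 is 2.2% at a true proportion of 0.80, and power at 0.90 is 92.8%. With 137 pairs the rule needs 119, with 2.4% and 91.0%.

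**Worst case for exclusions, 150 pairs.** Suppose up to k failing pairs can be removed and no successful pair is. The study is then positive whenever the successes among the original 150 reach the minimum required for 150 − k pairs. The last column is P(X ≥ minimum) for X binomial with 150 trials and probability 0.80.

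| Failing pairs dropped (k) | Pairs left | Minimum successes | Chance of a positive study at 0.80 |
|---|---|---|---|
| 0 | 150 | 130 | 2.2% |
| 1 | 149 | 129 | 3.7% |
| 2 | 148 | 128 | 5.9% |
| 4 | 146 | 127 | 8.9% |
| 5 | 145 | 126 | 12.9% |
| 10 | 140 | 122 | 38.7% |

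With 137 pairs the chance is 4.1% for one or two drops, 10.1% for four and 14.7% for five.

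**Drops needed to reverse a failed result.** 129/150 needs one, 128/150 needs two, 127/150 needs four and 126/150 needs five. One to five exclusions are 1/150 = 0.7% to 5/150 = 3.3% of pairs, and they reverse a failure at observed agreement of 84% to 86%. A clear failure such as 122/150 (81.3%) needs ten.

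**The case against.** The strongest objection is that the protocol nowhere says the decision is taken with the paired values in view. A reader might infer this from the Sponsor's roles, but the text does not support it. What section 16.8.1 sends to the Sponsor is the details of the deviation. The site must notify immediately, so a decision could come before eCRF entry, for which about a week is allowed. Access is limited to analysis staff, and the protocol does not say that one of them makes the decision. This stands, and the point is limited to the absence of any barrier.

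A reader might also infer that deviations will be common because subjects move, talk, recline or wear loose clothing. Section 11.0 lists movement, talking and clothing as observations to record, and sections 7.2 and 20.2 permit reclining with the angle noted. These are not deviations. Nor do the documents show that deviations cluster where the device reads badly.

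Nor can it be said that the site has no means of checking. Section 14.11 states that "The investigational site team at CUH will be given the results of the study but will not have access to the raw data". Even so, section 11.0 has the site write both device and reference results on its own visit record and receive the Breath Scan PDF, and section 11.1 has it keep source documents. Deviation forms, external audit and Ethics Committee reporting add traceability. These measures allow exclusions to be traced afterwards, but they do not govern which pairs are excluded.

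Finally, analysis sets are often left to a separate plan, and keeping every pair as primary is not the only defensible choice. Both are true, but a later plan would have to override a rule that section 16.8.1 already states.

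**Conclusion.** The concern holds in this form: for uncorrectable deviations the protocol gives the Sponsor an exclusion decision with no pre-specified criteria, timing or blinding, nothing prevents it from being informed by the paired values, and no planned analysis shows the result with excluded pairs restored. With 150 pairs, one exclusion can turn 129 successes from a failure into a pass.

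The error rates of 3.7%, 5.9% and 12.9% for one, two and five drops are ceilings, not forecasts. They assume that only failing pairs are dropped, that each has an uncorrectable deviation that could be cited, and that k takes the stated value. They do not show that the Sponsor would act in this way. The point concerns outcomes near the boundary; a clear failure would need about ten such exclusions.

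**What to change.** Amend section 16.8.1 and section 14 together:

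1. The primary PEF proportion keeps every valid pair, whatever its deviation status.
2. Exclusions for deviations are confined to a sensitivity analysis, using deviation types listed before first enrolment.
3. The exclusion list is decided from the description of the deviation alone, by someone not given the measured values, and is locked before the analysis is run. The investigator and the monitor do not suit this role: the site records both values on the visit record, and the monitor verifies source data.
4. The report gives the number of exclusions, how many of those pairs lay within and outside ±20%, and the results with and without them.

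The cost is protocol wording and a deviation listing prepared without measured values. The downside is that a few poor-quality pairs stay in the primary proportion and may lower it slightly.

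Separately, reconcile sections 11.0 and 18.2. The first treats the handwritten visit record as the source for the Breath Scan, with the PDF as verification; the second treats the cloud data as the source and the handwriting as backup. Section 18.2 adds that if the two records differ, "the Sponsor will be notified and asked to review the raw data to confirm correctness". It mentions no reference value, so it does not show that discrepancies are settled with the spirometer result in view.
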